8.2. Protocol Deviations

Identification of important protocol deviations may be derived from data or may be from observation from clinical monitoring. All patients with important protocol deviations or major protocol deviations, will be summarized by randomized arm. In addition, the listing of patients excluded from PP population along with the corresponding reason will be provided.

8.3. Duration of Follow-Up

The duration of follow-up is defined as the time from randomization to the last known alive date.

9. Demographics and Baseline Characteristics

9.1. Demographics

The demographic characteristics will be summarized by randomized arm and overall for ITT, Safety populations. The demographic characteristics consist of age, sex, race, ethnicity, height, weight, body surface area (BSA), body mass index (BMI), and ECOG PS.

9.2. Baseline Disease Characteristics

Cancer history data will be summarized and listed, including metastatic pancreatic cancer at baseline (Yes or No), time from initial diagnosis to randomization (months), stage at initial diagnosis, locally advanced or metastatic stage cancer at initial diagnosis (Yes or No), prior radiation therapy (Yes or No), prior Whipple procedure (Yes or No), prior biliary stent performed (Yes or No), location of the primary lesion(s) in the pancreas, histology of pancreatic cancer (Adenocarcinoma or Other), number and location of metastatic sites at screening will be summarized by randomized arm and overall.

9.3. Prior Systemic Cancer Therapy

The number of prior systemic cancer therapy regimens patient received, prior systemic cancer therapy (by regimen), intent of prior cancer therapy (Adjuvant/Neo-Adjuvant or Advanced/Metastatic), duration of prior cancer therapy (months), the best response to the prior systemic cancer therapy, time from progressive disease of first line therapy to randomization (days), reason for discontinuation, instrument used to measure the PD will be summarized by randomized arm.

9.4. Medical History

Medical history terms will be coded using the latest version of the Medical Dictionary for Regulatory Activities[MedDRA].

A summary for medical history will be presented including the count and percent of patients with any medical history record and also by body system and Preferred Term (PT).

10. Treatments and Medications

10.1. Concomitant Medications

Concomitant medications will be coded using the most recent version of World Health Organization (WHO) Drug Dictionary. Concomitant medications are defined as

- The medication was started on or after the date of first dose of study treatment and before treatment discontinuation date + 30day;
- The medication was started prior to first dose study treatment but was ongoing at the time of the first dose of study treatment.

Concomitant medications will be summarized separately and presented by drug class and PT by randomized arm on safety population. In addition use of selected concomitant medication, such as steroid, use will be summarized separately. Study Treatments

All study treatment summaries will be based on the Safety population.

10.1.1. Treatment Exposure

The following parameters will be summarized by treatment arm:

Overall Treatment:

- duration of treatment (months):
 - \circ Pegilodecakin: (last dose date first dose date+1)/ 30.4375
 - Any component of FOLFOX: (last dose date first dose date + 14)/30.4375
- number of cycles administered (patient with total number of cycles administered, 1 cycle, 2 cycles, 3 cycles, etc.)
- total number of cycles administered

The following parameters will be summarized (descriptive statistics) by study drug component within each treatment arm:

- total cumulative dose (mg for pegilodecakin and mg/m² for each FOLFOX drug component)
- total dose per cycle (dose intensity)
- relative dose intensity (%), summarized by descriptive statistics and by categories of [60%, 80%), [80%, 100%), [100%, 120%) and ≥120%, etc.

In ARM 1(Pegilodecakin + FOLFOX), pegilodecakin's will be treated up to 12 cycles with 4 mg/cycle (2weeks) for patients with weight \leq 80 kg and 8 mg/cycle (2weeks) for patients with weight >80 kg. After the 12 cycle, patient receiving benefit on ARM 1 can continue on maintenance cycle with double of the dose 8 mg/2 weeks for patients with weight \leq 80 kg and 16 mg/2 weeks for patients with weight >80 kg. Therefore the exposure will be summarized in the following categories:

- for FOLFOX, exposure will only be summarized up to 12 cycles.
- for Pegilodecakin:
 - Cumulative dose, total dose per cycle and relative dose intensity will be summarized up to 12 cycle prior to maintenance period and repeated within the maintenance period.
 - The duration of treatment, and number of cycle administered will be summarized across all treatment durations and repeated for the maintenance cycle.

The key parameters used to calculate dosing data are shown in Table JZGB.10.1:

Table JZGB.10.1.	Patient Exposure Prior to Maintenance Period
------------------	--

		FOLFOX		
Treatment	pegilodecakin	Oxaliplatin	Leucovorin	5- FU
Planned Dose intensity	4 mg/cycle (14 days) (≤ 80kg) 8 mg/cycle (14 days) (> 80kg)	85 mg/m ² per cycle(14 days)	400 mg/m ² per cycle (14 days)	2800 mg/m ² per cycle (14 days)
Cumulative dose	sum of the doses mg for pegilodecakin, or mg/m^2 for FOLFOX administered to a patient during the treatment period			
Actual Dose intensity	Cumulative dose/ duration of treatment (mg/2week)	ration of treatment (mg/m ² /cycle)		
Relative dose intensity (%)	Actual Dose intensity/planned dose intensity			

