In all 21 patients (ITT population), the median PFS was 2.6 months and the median OS was 10.2 months. The 1-year survival was 42.9% ([Figure 3](#)).

[figure not shown]
Based on early results, a 5-µg/kg dose combined with FOLFOX is proposed for this Phase 3 trial. At this dose level, thrombocytopenia associated with the combination treatment is manageable and is associated with early evidence of efficacy.

The proposed dosing schedule (5 days on, 2 days off) is predicted from hematologic and biomarker analysis and modeling to mitigate the risk of thrombocytopenia while maintaining the activation of the immune system and clinical benefit. These findings support the selection of a 5/2 regimen to replace the daily SQ regimen administered in a previous clinical trial. This 5/2 regimen is expected to decrease the incidence and magnitude of thrombocytopenia and permit recovery of platelet counts during the 2-day off rest period.

The rationale for dosing at a flat rate with a cutoff at 80 kg is based on safety and on the PK/pharmacodynamic relationship. More specifically, immune activation with AM0010 requires a serum trough of at least 1 ng/mL. This minimal trough level is reached with actual doses of 2.5 µg/kg and higher. The maximum tolerated dose (MTD) of AM0010 monotherapy is 20 µg/kg.

In a Phase 1b study with AM0010 + FOLFOX, patients received individual weight-based doses of a median of 6.31 µg/kg AM0010 (range 4.19–9.11 µg/kg). Within this Phase 1b study, encouraging OS was observed in patients receiving more than 5 µg/kg, based on their individual weight. Safety and tolerability of AM0010 + FOLFOX was also explored in a dose escalation study, in which patients received up to 13.4 µg/kg. However, patients with doses above 10 µg/kg in combination with FOLFOX may have required dose reductions.

Table 9 provides the actual received dosage per kg for patients with weights between 40 and 160 kg. It shows that a safe and efficacious dose is obtained with the proposed flat rate dosing for patients above and below 80 kg.

AM0010 at 10 µg/kg was determined to be the optimal biologic dose for maintenance therapy. In 144 patients who received monotherapy in Phase 1 the MTD was determined to be 20 µg/kg as described in the IB. The pharmacodynamic analysis indicates immune activation at 10 µg/kg as monotherapy (Naing et al JCO, 2016). Therefore, AM0010 at 10 µg/kg was chosen for the maintenance dose.

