2.2.1 Treatment Duration

Each cycle is 14 days, with Days 6, 7, 13, and 14 being rest days for AM0010. FOLFOX will be administered on Day 1 of each cycle. Patients randomized to the investigational combination treatment (AM0010 plus FOLFOX) ARM 1, after completion of up to 12 cycles of combination chemotherapy or if experiencing chemotherapy intolerance (as defined as Grade 3 or 4 non-hematologic toxicity that has not resolved to baseline in 28 days or Grade 4 hematologic toxicity that has not resolved to baseline in 28 days) may continue to receive maintenance AM0010 if the patient continues to receive clinical benefit (CR, PR, or SD). Patients may receive FOLFOX on both study arms for up to 12 cycles or 24 weeks. Patients will be treated until tumor progression by RECIST v.1.1.

Patients may continue on treatment until they experience progressive disease, unacceptable toxicity, require palliative radiotherapy, withdraw consent, or their physician feels it is no longer in their best interest to continue on study treatments.

To mitigate the chance of detecting false-progression (ie, pseudoprogression) early in the course of treatment on ARM 1 with AM0010 in combination with FOLFOX, patients whose scans show radiographic progression in the absence of clinical deterioration including worsening ECOG PS as assessed by the Investigator may remain on study treatments and should have an additional scan 4

weeks (± 3 days) later as outlined in Section 8.1.1. If this subsequent scan shows disease progression, the patient will be discontinued from study treatments.

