5.2.2 AM0010 and FOLFOX Dose Modifications

If a patient experiences any of the following treatment-related toxicities, dosing will be postponed until the toxicity has resolved to Grades 0–1 (as defined by NCI CTCAE v4.03) or returns to the patient's baseline value. Re-initiation of therapy may occur during a cycle of therapy or at the beginning of the next cycle of dosing. Dose reductions for AM0010 plus FOLFOX are shown [Table 13](#).

Table 13: Dose Reduction Levels for AM0010 plus^a FOLFOX

| FOLFOX | Dose Level | | | |
|---|---------------------------------|--------------------------------|--------------------------------|------------------------|
| | Starting Dose | -1 | -2 ^b | |
| Oxaliplatin | 85 mg/m ² | 65 mg/m ² | 50 mg/m ² | 50 mg/m ² |
| 5-FU bolus | 400 mg/m ² | Omit | Omit | Omit |
| 5-FU continuous infusion over 46–48 hours | 2400 mg/m ² | 1900 mg/m ² | 1500 mg/m ² | 1500 mg/m ² |
| dl-Leucovorin/l-Leucovorin ^c | 400 mg/m ² | 100% | 100% | 100% |
| AM0010 | Dose Level | | | |
| | Starting Dose | -1 | -2 | |
| | 100% (5 days on and 2 days off) | 80% (4 days on and 3 days off) | 60% (3 days on and 4 days off) | |

^aIf an AE is believed likely to be due to 1 drug, it is permissible to decrease dose of that drug only.

^bFurther dose levels (-3, -4, etc.) will be 20% dose reductions from the previous level for oxaliplatin and 5-FU continuous infusion. In addition, the bolus dose of 5-FU will continue to be omitted, and the leucovorin dose will remain unadjusted (100%).

^cDosing of leucovorin will remain fixed at 100% of the recommended dose. Non-racemic L-leucovorin dose is 200 mg/m².

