5.3 Study Treatment Dose Delays

Patients who do not meet the minimum re-treatment criteria on Day 14 (± 3 days) of the cycle and do not meet the criteria for discontinuation will delay treatment and be followed for resolution of toxicity to levels specified in the package insert for resuming FOLFOX. Cycles may also be delayed for logistic or personal reasons, but patients who have not received therapy for 28 days from the scheduled start of cycle should be discontinued from AM0010 and/or FOLFOX treatment unless:

1. The patient is clinically benefiting from therapy, defined as radiographic or symptomatic improvement in the opinion of the Investigator, and
2. Approval is obtained from Lilly or Lilly's designee Medical Monitor in collaboration with the Investigator. Study treatment should be discontinued for any dose delay greater than eight weeks (>56 days).

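### SAP Table JZGB.10.1 leaves the rest days after the last pegilodecakin dose out of the dose-intensity denominator, so relative dose intensity is slightly overstated (116.7% for one fully compliant cycle, 101.2% for twelve)

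*SAP*

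**What the plan says.** SAP 10.1.1 gives two duration rules, both in months. For pegilodecakin, the last dose date less the "first dose date+1)/ 30.4375" (the minus sign is lost in the text). For any FOLFOX component, the last dose date less the "first dose date + 14)/30.4375". The first stops on the day of the last injection; the second credits the whole last cycle.

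Table JZGB.10.1 sets planned pegilodecakin intensity at 4 mg (≤80 kg) or 8 mg (>80 kg) per 14-day cycle. Actual intensity is "Cumulative dose/ duration of treatment (mg/2week", and relative dose intensity (RDI) is actual over planned. RDI is also reported in bands with cuts at 60%, 80%, 100% and 120%.

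The same section lists "total dose per cycle (dose intensity" as a parameter, which is a second definition under the same name.

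Protocol 2.2.1 describes a 14-day cycle, "with Days 6, 7, 13, and 14 being rest days for AM0010" (AM0010 is pegilodecakin). The last scheduled dose of a cycle is therefore on Day 12.

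**The concern.** The numerator and the plan cover whole 14-day cycles, but the denominator ends two days before the last cycle does. A patient who takes exactly the planned dose is reported above plan, and the excess is largest in patients who stop early. Two programmers following the same section could also report different dose intensities for the same patient.

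Protocol 7.6.1 promises an analysis of the percentage of planned dose given before discontinuation. In SAP 10.1.1, RDI is the only measure expressed as a percentage of plan, and its bands have a cut at exactly 100%, so a small upward shift can move patients between bands.

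**Working it through.** **Inputs.** 0.4 or 0.8 mg per injection (SAP 6.3); 10 injections per cycle, on Days 1–5 and 8–12; duration and intensity rules from SAP 10.1.1 and Table JZGB.10.1. Duration in months times 30.4375/14 gives 14-day units, which the table's mg/2week unit requires.

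**Planned figure reproduced.** 10 × 0.4 = 4 mg and 10 × 0.8 = 8 mg per cycle, matching the table. The weight band cancels in RDI, so the ≤80 kg case is used below.

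**Fully compliant, no net delay, n cycles.** Duration = 14(n − 1) + 12 = 14n − 2 days. RDI = [4n / ((14n − 2)/14)] / 4 = 14n/(14n − 2).

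| Cycles | Days counted | RDI |
|---|---|---|
| 1 | 12 | 116.7% |
| 2 | 26 | 107.7% |
| 4 | 54 | 103.7% |
| 6 | 82 | 102.4% |
| 8 | 110 | 101.8% |
| 12 | 166 | 101.2% |

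Total dose per cycle gives 4/4 = 100% at every n. The FOLFOX rule, with duration 14(n − 1) + 14 = 14n days, also gives 100%. That last result is inferred from the duration rule, because the FOLFOX actual-intensity cell is broken in the text available.

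**Net delay of d days, all doses given.** Protocol 5.3 allows this: "Cycles may also be delayed for logistic or personal reasons". RDI = 14n/(14n − 2 + d). With d = 2 it is exactly 100.0% at every n, so the omitted days hide up to two days of delay. With d = 3 it is 14/15 = 93.3% (n = 1) and 168/169 = 99.4% (n = 12).

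**One missed mid-course dose, no delay.** RDI = 1.4(10n − 1)/(14n − 2). For n = 1, 12.6/12 = 105.0%, against 9/10 = 90% by dose count. For n = 12, 166.6/166 = 100.4%, against 119/120 = 99.2%. Both patients move from the 80% to under 100% band into the next one up.

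**Stop in the first dosing week after k doses (k = 1 to 5), none missed.** RDI = [0.4k/(k/14)]/4 = 140%, which falls in the top band with no excess dose given.

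**Realistic scale.** For the Phase 1b pancreatic cohort, Protocol 1.3.2 reports that "the median PFS was 2.6 months and the median OS was 10.2 months". Taking PFS as a proxy for treatment time, 2.6 × 30.4375 = 79.1 days, or 5.65 cycles, and 79.1/77.1 = 1.026: about 2.6 points. The same section says 9 of 21 patients were treated for more than 16 weeks (8 cycles); for a compliant patient treated that long the excess is below about 1.8 points.

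**The case against.** **The denominator is undefined, not wrong.** Duration is in months, the table's unit is two weeks, and the section elsewhere speaks of dose per cycle. If the denominator is read as cycles, the section agrees with itself and RDI is 100%. But the table's words are duration of treatment, which the section defines by dates, and converting months to 14-day units only honours the table's own unit. SAP 7.6 places further data-handling rules in a separate programming document; nothing in the SAP indicates that they cover this.

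**The +1 rule is reasonable for a near-daily drug, and +14 for a once-per-cycle drug.** As a measure of duration, yes, and the reported duration need not change. The mismatch arises only when that duration is divided into a plan that includes rest days.

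**Scope of the figures.** This objection stands. The SAP gives no separate pre-maintenance duration, so 101.2% at 12 cycles for a patient entering maintenance assumes a cut at the last pre-maintenance dose. Table JZGB.10.1 is titled as covering the period before maintenance. Applying its formula in maintenance (16/(26/14)/8 = 107.7% after one 28-day cycle) is therefore an extrapolation, although SAP 10.1.1 does repeat RDI there.

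**Stronger readings that the documents do not support.** A reader might infer that compliant patients are put in the wrong band. Those who complete the cycle are not: 100%, 101.2% and 116.7% all lie in the 100% to under 120% band. A reader might infer from SAP 10.1.4, which confines interruptions to FOLFOX components and tabulates them for the FOLFOX arm, that pegilodecakin holds go unreported. SAP 10.1.3 summarizes delays for each drug component in each arm, so that point is largely terminology, plus one arm missing from the interruption table.

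**Conclusion.** The point holds in a limited form. As written, the table's formula overstates pegilodecakin RDI and conflicts with the per-cycle definition in the same section. The excess for a fully compliant patient is 16.7 points at one cycle, 3.7 at four and 1.2 at twelve. Band changes are confined to patients such as early stoppers or those with a missed dose or a short delay.

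The importance is minor. Only descriptive exposure tables are affected, and cumulative dose and cycle counts appear alongside. OS, alpha and sample size are untouched.

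The figures assume the lost minus sign is restored, months are converted to 14-day units, and, except for the first-week stops, the last dose falls on Day 12 of the last cycle. The 12-cycle figure also needs the unstated pre-maintenance cut-off.

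**What to change.** Leave the reported duration of treatment as it is. For pegilodecakin RDI only:

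- Use as denominator the days from first dose to the end of the last started 7-day dosing week, divided by 14. Count that week from the restart day if dosing resumes mid-cycle, since Protocol 5.2.2 says "Re-initiation of therapy may occur during a cycle of therapy or at the beginning of the next cycle of dosing".
- State the date that separates the pre-maintenance from the maintenance period, and apply the same rule within maintenance against the SAP's plan of 8 or 16 mg per 14 days.
- Align the per-cycle total with this definition, or remove the dose-intensity label from it.

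With no net delay, completed cycles then score 100%, 80% and 60% on the protocol's three dosing schedules, and a compliant 28-day maintenance cycle scores 16/(28/14)/8 = 100%.

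The simpler denominator of 14 days times cycles started should be avoided, or restricted to the pre-maintenance period: a compliant 28-day maintenance cycle would score 16/(14/14)/8 = 200%.

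The cost is a small wording and table-shell edit, using dosing data already collected. RDI becomes slightly less favourable. Patients who stop mid-week score lower: 0.4/(7/14)/4 = 20% after one dose. One day of net delay over 12 cycles scores 168/169 = 99.4%, although Protocol 6.2.1.1.2 allows ±3 days per FOLFOX cycle. RDI should therefore be read with duration and cumulative dose.

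Two secondary clarifications:

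- State planned leucovorin intensity by formulation, as Protocol 5.1.2 already gives it. The table has 400 mg/m² for everyone, so a patient on the l-form at 200 mg/m² would score 200/400 = 50% unless converted.
- Reconcile SAP 10.1.4 with Protocol 7.6.1, so that interruptions are summarized for each arm.

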5.1.2 FOLFOX Administration

FOLFOX treatment will be continued for up to 12 cycles or until disease progression or unacceptable chemotherapy-related toxicity. The FOLFOX dosing regimen will consist of *dl*-LV 400 mg/m^2 and oxaliplatin 85 mg/m^2 followed by bolus 5-FU 400 mg/m^2 and a 46- to 48-hour infusion of 5-FU 2400 mg/m^2 . Note: if the institution is using l-LV (non-racemic), the dose is 200 mg/m^2 .

Prior to and during the treatment with either oxaliplatin or 5-FU at the beginning of each treatment cycle, premedication may be given per institution standard for the prophylaxis of nausea, vomiting, and diarrhea or following the guidelines below.

A 5-hydroxytryptamine-3 (5-HT₃) antagonist (eg, ondansetron or granisetron) and dexamethasone may be administered for the prophylaxis of nausea and vomiting. Dexamethasone (10 to 20 mg) may be administered as an IV bolus administered over 30 to 60 seconds.

For preparation and complete prescribing information, refer to the most current prescribing information in the region. Immune and chemotherapy regimens should be applied following the

guidelines in the protocol or established institutional practices. Investigators or designees will review the patient's hematology and chemistry panels, liver function tests, and the incidence of hematologic and non-hematologic toxicities prior to and during chemotherapy regimens.

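### SAP Table JZGB.10.1 has one planned leucovorin dose, 400 mg/m², so a fully dosed l-leucovorin patient (200 mg/m² in the protocol) would read 50% relative dose intensity if the dose is recorded as given

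*SAP*

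**What the plan says.** SAP 10.1.1 summarizes cumulative dose, dose per cycle and relative dose intensity "by study drug component within each treatment arm", so leucovorin has its own rows. In Table JZGB.10.1:

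- The planned leucovorin intensity is "400 mg/m ² per cycle (14 days"), with no split by product. SAP 6.3 likewise lists only dl-leucovorin at 400 mg/m².
- Cumulative dose is the sum of what was "administered to a patient during the treatment period", in mg/m² for the FOLFOX drugs.
- Relative dose intensity is "Actual Dose intensity/planned dose intensity". It is also reported in bands. The lowest band named is 60% to under 80%, and the list ends in etc.

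Protocol 5.1.2 gives dl-leucovorin 400 mg/m² in the standard regimen and then adds: "if the institution is using l-LV (non-racemic), the dose is 200" mg/m². Footnote c of Table 12, of Table 13 and of the Appendix D reduction table repeats 200 mg/m² for the non-racemic product. The same footnotes hold leucovorin at its full recommended dose at every FOLFOX reduction level. Protocol 5.2.1 and Appendix D also allow institutional adjustment in a supply shortage.

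The SAP mentions neither l-leucovorin nor a conversion.

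**The concern.** The protocol permits two leucovorin products with planned doses that differ by a factor of two, and the SAP has a denominator for only one. The table can handle a planned dose that varies by patient: its pegilodecakin cell carries two values, by body weight. Leucovorin needs the same treatment and does not get it.

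What is at stake is whether the leucovorin exposure summaries can be read. A patient who received the full planned l-leucovorin dose would look half-dosed. A dl-leucovorin patient whose dose really was halved, for instance in a supply shortage, would read 50% as well, so the table could not separate under-delivery from choice of product.

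**Working it through.** **Inputs**

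- Planned leucovorin intensity: 400 mg/m² per 14-day cycle (SAP Table JZGB.10.1).
- Planned dose by product: dl-leucovorin 400 mg/m², l-leucovorin 200 mg/m² (protocol 5.1.2; footnote c of Tables 12 and 13 and of the Appendix D table).
- Cycles: up to 12 of 14 days (protocol 5.1.2 and 5.1.3).
- FOLFOX duration: last dose date minus first dose date plus 14 days (SAP 10.1.1). Twelve on-time cycles give 11 × 14 + 14 = 168 days, or 168/14 = 12 cycles.

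**Formulas**

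Actual intensity = cumulative dose / number of cycles. Relative dose intensity = actual / planned.

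The SAP states duration in months but labels FOLFOX intensity per cycle. I used cycles. The choice of time unit scales both products equally and leaves the 2:1 ratio unchanged.

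**The plan's own figures first**

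- dl-leucovorin: 12 × 400 = 4800 mg/m²; 4800/12 = 400 per cycle; 400/400 = 100%.
- 5-FU: 400 + 2400 = 2800 mg/m², as in the table.
- Pegilodecakin: 10 doses per cycle × 0.4 mg = 4 mg, and 10 × 0.8 mg = 8 mg, as in the table.

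So the 400 reproduces, as the dl-leucovorin dose.

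**l-leucovorin under the same rule, full dose and on time**

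- 12 × 200 = 2400 mg/m²; 2400/12 = 200 per cycle; 200/400 = 50%.
- The number of cycles cancels. One cycle gives 200/400, and four give (800/4)/400, both 50%.
- With a denominator of 200 the same patient reads 200/200 = 100%.

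**Effect on the means**

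Let p be the share of patients on l-leucovorin. The documents do not give it, so the values below are assumptions. With everyone fully dosed for 12 cycles:

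- mean relative dose intensity = 100% − 50% × p
- mean dose per cycle = 400 − 200 × p
- mean cumulative dose = 4800 − 2400 × p

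| p | Mean relative dose intensity | Mean dose per cycle (mg/m²) | Mean cumulative dose (mg/m²) |
|---|---|---|---|
| 10% | 95% | 380 | 4560 |
| 30% | 85% | 340 | 4080 |
| 60% | 70% | 280 | 3360 |

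**Between arms**

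The artefact in the difference of means is 50% × (p in one arm − p in the other). Product is chosen by institution and randomization is 1:1, stratified by region, so the shares should be close. A chance imbalance of 5 percentage points would move the difference by 2.5 points.

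**The case against.** The mismatch is hard to dispute. The strongest opposing case concerns its consequences, and most of that case stands.

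- **Delivery of the FOLFOX backbone.** A reader might infer that the plan misreports how well FOLFOX was delivered, and so casts doubt on the adequacy of the control arm. The documents do not support that. Oxaliplatin and 5-FU have their own correct denominators, no composite FOLFOX intensity is planned, and delays and reductions are reported per component (SAP 10.1.3 and 10.1.4.1).
- **Regional differences.** A reader might expect delivery to appear to differ by region or site. No such exposure table is planned. SAP 10.1.1 summarizes by arm. Region is a subgroup for OS and PFS (SAP 11.1.1 and 11.2.1), and adverse-event subgroups are age, gender and race (SAP 12.1).
- **Unclassified patients.** It is tempting to say that 50% falls outside the reporting bands. Because the list ends in etc., a lower band is not excluded.
- **Leucovorin always at 100%.** That holds across toxicity reductions, but the supply-shortage allowance qualifies it.
- **The error may never occur.** The 200 mg/m² dose is conditional on institutional practice, so p could be zero. A conversion might exist in the CRF or in the separate programming specifications mentioned in SAP 7.6. This limits certainty about what would be reported. It does not remove the defect: SAP 7.6 describes no conversion, and the denominator is defined in the SAP table itself.

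**Conclusion.** The point holds, with limited reach. As written, the rule returns 50% where 100% is meant for every fully dosed, on-time l-leucovorin patient, and it averages two scales in the other leucovorin dose summaries.

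This rests on two assumptions: that l-leucovorin is entered as mg/m² given, and that 200 mg/m² is its planned dose, as protocol 5.1.2 and the footnotes state. The effect on the mean depends on p: from 95% down to 70% for assumed shares of 10% to 60%, against a true 100%.

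Only descriptive leucovorin exposure is affected. Oxaliplatin, 5-FU and pegilodecakin exposure, treatment duration, cycle counts and all tests of OS, PFS and ORR are unchanged, and the between-arm comparison of leucovorin is largely preserved. It is a correction worth making, but no conclusion about efficacy depends on it.

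**What to change.** Give the leucovorin cell of Table JZGB.10.1 one planned intensity per product, taken from the protocol's own planned doses, in the way the pegilodecakin cell is split by weight. Alternatively, define a conversion to one scale (on the protocol's doses, l-leucovorin mg/m² × 2 gives dl-equivalents) and apply it before computing relative dose intensity. Present cumulative dose and dose per cycle by product or on that scale, and state the choice in a footnote.

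The SAP text and programming are small changes. The real condition is data: the documents do not show that the CRF captures which leucovorin was given. If it does not, the form must come from the drug or pharmacy record, or be queried by institution.

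The protocol should be made consistent as well. The combined dl-/l-leucovorin rows of Tables 12 and 13 and of the Appendix D table show 400 mg/m² and leave 200 mg/m² to a footnote. Footnote r of the Appendix A schedule writes l-dl-LV at 400 mg/m². These places and Section 5.1.2 need to be reconciled by the sponsor, and the SAP denominators should follow the reconciled text.
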